3.3.1.2.1 Baseline Six-Minute Walk Test

The 6MWT performed at Baseline must be conducted prior to the first dose of oral treprostinil. If a practice 6MWT is conducted at Screening, the Baseline 6MWT must be conducted at least one day apart. For the purposes of the 6MWT, if the subject was assessed

at Baseline using oxygen therapy, then all 6MWTs during the 24-week study should be conducted with the same oxygen flow rate and mode of administration. The 6MWT should be conducted at least two hours prior to conducting the CPET.

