1.2.3 Clinical Pharmacology

The absolute bioavailability following administration of the oral treprostinil extended release tablet is 17% compared with IV Remodulin. Maximum treprostinil concentrations occur between approximately 4 and 6 hours following administration of oral treprostinil in adults.

Following administration, oral treprostinil is widely distributed. Oral treprostinil is approximately 96% protein bound with no effect on warfarin or digoxin displacement. Pharmacokinetic area under the curve (AUC) data; indicate that Day 1 data are predictive of Day 13 and linearity was observed in plasma exposure comparing 1 mg and 2 mg doses in healthy volunteers. Food, particularly a high calorie meal, has been observed to increase absorption and prolong exposure, contributing to the desired pharmacokinetic profile. The relative bioavailability of treprostinil following oral administration of a 1 mg extended release tablet was not significantly altered by meal types ranging from 250 to 500 calories in healthy adult volunteers.

Treprostinil is primarily metabolized by cytochrome (CYP) 2C8 and to a lesser extent by CYP2C9. It is unknown if the metabolism of oral treprostinil will be altered in pediatric patients. A study evaluating the metabolism of paclitaxel by CYP2C8 using pediatric and adult liver microsomes found no age-related differences in metabolism [Blanco, 2000]; however, CYP2C9 activity appears to be increased in children. Clearance is approximately twice that of adult values for several drugs predominately metabolized by CYP2C9, including warfarin, phenytoin, and celecoxib [Anderson, 2009]. Co-administration of oral treprostinil with a strong CYP2C8 inhibitor (*e.g.*, gemfibrozil) has been demonstrated to result in significant elevation of treprostinil plasma concentrations.

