- ^g cMRI is optional for children younger than 10 years of age. Must be performed prior to 6MWT and CPET if done on the same day. If subject requires anti-anxiety medication (no general anesthesia) during the cMRI (without contrast), then the cMRI should be performed on a separate day from the CPET and 6MWT.
- ^h Blood for NT-pro-BNP assessment must be drawn prior to conducting the 6MWT or CPET and will occur prior to the first dose of oral treprostinil at Baseline (or as part of the Screening visit assessment if the Screening and Baseline visits are combined).
- ⁱ 6MWT is only required at Screening if the subject has not previously undergone a 6MWT/Borg dyspnea score at the study site. In that case, a practice test must be conducted and must precede the Baseline 6MWT by at least one day. The 6MWT at Baseline must be conducted prior to the first dose of oral treprostinil. Screening (if applicable) and Baseline 6MWTs will also include oximetry and HR recovery monitoring.
- ^j 6MWT should occur within 2-6 hours of the subject's last dose (i.e., most recent dose) of oral treprostinil and should be performed at least two hours before the CPET when they are performed at the same day. This will include oximetry and HR recovery monitoring.
- ^k CPET should be performed a minimum of two hours after the 6MWT. At Week 24, the CPET should be performed 2-6 hours after the morning dose of oral treprostinil. It may be waived for subjects less than 130 cm in height, based on equipment available at the center.

United Therapeutics Corp.

- ¹ Administration of the oral treprostinil dose on the day of Week 24 PK sampling should occur approximately 8 hours after the prior evening's last oral treprostinil dose for subjects using the morning dose for the PK assessment. When using the midday dose for the PK assessment, the midday dose of oral treprostinil should occur approximately 4 to 6 hours after that day's morning dose. No oral treprostinil dose changes are allowed within five days of the Week 24 PK sampling, unless required to protect subject safety. See Section 3.3.3 and Section 15.5.

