3.3.1.2.2 Treatment Six-Minute Walk Tests

The 6MWTs will be conducted during each day of the inpatient hospital stay (Cohort 1 subjects only) and all subsequent study visits, and should occur within 2-6 hours of the subject's last dose (i.e., most recent dose) of oral treprostinil. Subjects receiving supplemental oxygen during the Baseline 6MWT must continue to receive the same flow rate and mode of oxygen therapy at all subsequent 6MWT assessments. The 6MWT should be performed at least two hours prior the CPET at Week 24/Premature Termination.

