4.1 INCLUSION CRITERIA

A subject is eligible for inclusion in this study if all of the following criteria apply:

- 1. Legal guardian informed consent and subject assent, if appropriate, to participate in the study is voluntarily given.
- 2. The subject is between 7 and 17 years of age, inclusive, on the date informed consent is signed.
- 3. *Cohort 3:* The subject must weigh a minimum of 22 kg at Screening.
- 4. The subject has a current diagnosis of PAH (WHO Group I) associated with:
 - a. Idiopathic or heritable PAH
 - b. Persistent PAH for at least one year following surgical repair of a congenital systemic-to-pulmonary cardiac shunt, congenital heart disease, or other congenital heart lesions with no clinically significant residual defects and condition is stabilized hemodynamically
 - c. PAH in subjects with unrepaired restricted atrial septal defect, ventricular septal defect, or patent ductus arteriosus; subject must have a resting postductal oxygen saturation (off oxygen) of greater than 88%
- The subject has a current diagnosis of PAH confirmed by right heart catheterization (RHC) prior to the Screening visit with the following parameters:
 - a. Mean pulmonary arterial pressure (mPAP) of ≥25 mmHg
 - b. Pulmonary vascular resistance index (PVRi) of >3 Wood Units * m²
 - c. Left ventricular end diastolic pressure (LVEDP) or pulmonary capillary wedge pressure (PCWP) of ≤15 mmHg

- 6. Cohort 1: The subject must have been receiving IV/SC Remodulin for at least 90 days without dose change for at least 30 days prior to Baseline. The IV/SC Remodulin dose will be between 25-75 ng/kg/min, inclusive, for the first five subjects in the cohort. Following a safety review, the dose range may be expanded to 25-125 ng/kg/min, inclusive, for the remaining subjects. Subjects must be receiving stable doses of all other PAH medications for at least 14 days prior to the Baseline assessments; exception for diuretics and anticoagulants as outlined in Section 4.3.1.
- 7. Cohort 2: The subject must have been receiving inhaled prostacyclin for at least 90 days and has been at the current stable dose without changes for at least 30 days prior to Baseline. Subjects must be receiving stable doses of all other PAH medications for at least 14 days prior to the Baseline assessments; exception for diuretics and anticoagulants as outlined in Section 4.3.1.

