6.1.2 Cohort 2: Inhaled Prostacyclin to Oral Treprostinil Transition

Once all entry criteria have been met and Baseline assessments completed, dosing of oral treprostinil will be initiated at 0.125 mg TID or QID at the discretion of the Investigator, with food. Dosing will take place approximately every 6 to 8 hours for TID dosing or approximately every 4 to 6 hours for QID dosing, with adjustments permitted based on the subject's lifestyle and schedule. The first dose of 0.125 mg oral treprostinil should be taken at the study site. A cross titration will occur so that doses of inhaled prostacyclin will be decreased as oral treprostinil is increased. The transition must be completed by Week 4, or the subject will be withdrawn from the study.

Oral treprostinil dose escalations may occur every 24 hours (following three or four consecutive doses depending on TID or QID dosing, respectively) and should occur in increments of 0.125 mg TID or QID, at the discretion of the Investigator, during the first four weeks of the study as clinically indicated. Following four weeks of treatment, dose escalations may occur in either 0.125 mg or 0.25 mg increments every 24 hours, as tolerated. Sudden dose escalations or reductions should be avoided as they may lead to intolerable adverse effects or worsening of PAH. Gradual dose titrations are recommended to reduce the risk to subjects.

Routine contact between site personnel and the subject/caregiver should be conducted to monitor AEs and make decisions about dose titration between scheduled study visits. Dose

Version: Amendment 2_FINAL_01Sep2016

changes may be made at any time up until five days prior to the Week 24 visit. Week 24 visit assessments can be performed over five days (120 hours) if needed; however, no oral treprostinil dose adjustments are allowed from five days prior to the Week 24 study visit, unless required to protect subject safety. All dose changes will be documented and captured in the eCRF.

6.1.3 Cohort 3: Addition of Oral Treprostinil to Background PAH Therapy (De Novo Prostacyclin Subjects)

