### 10.3 SIX-MINUTE WALK TEST

The 6MWT is performed at Screening (optional), Baseline, Week 0 (Cohort 1 only), Week 3, Week 6, Week 12, and Week 24 or premature termination. At each of these visits, 6MWT recovery monitoring (heart rate and oxygen saturation measurements) will occur immediately prior to walk, immediately upon stopping the walk, 1 minute post walk, 2 minutes post walk, and 3 minutes post walk. The listing of 6MWT will include the assessment date/time; any Remodulin, oral treprostinil, Tyvaso, and Ventavis dosing information prior to the 6MWT assessment, as applicable; as well as whether subject attempted walk test (yes/no), reason not attempted (if applicable), total distance walked, Borg dyspnea score, oxygen receipt, and unusual circumstances. Recovery monitoring data (time point, heart rate, oxygen saturation, and total recovery time [minutes]) will be listed separately.

The summary of 6MWT will include the number (percentage) of subjects who received oxygen during the test and experienced any unusual circumstances during the test for each cohort.

The summary of 6MWD will include descriptive statistics for total distance walked by assessment visit and time point for each cohort. Changes from Baseline to each post-Baseline time point in total distance walked will also be summarized by cohort and compared within cohort using a Wilcoxon signed-rank test. P-values will be calculated for descriptive purposes; no formal hypothesis testing is planned.

As a sensitivity analysis, total walk distance data will be imputed using the LOCF method, regardless of the reason for early termination. The summary based on this imputation will follow the same layout as the no imputation analysis described above, while again using the Wilcoxon signed-rank test for descriptive purposes; no formal hypothesis testing is planned.

The summary of 6MWT recovery monitoring will include descriptive statistics for each cohort of heart rate (bpm) and oxygen saturation (%) at each of the 5 time points of assessment at each visit, as well as descriptive statistics of total recovery time (minutes).

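### In Cohort 2 the Baseline walk and CPET have no set time from the last inhaled session, so change from Baseline may mix assessment timing with the effect of the switch, in either direction

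*Protocol*

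**What the plan says.** **Baseline.** Section 3.3.1.2.1 of the protocol ties the walk to study drug in one way: "The 6MWT performed at Baseline must be conducted prior to the first dose of oral treprostinil". The footnote to the Cohort 2 and 3 schedule (Table 3-2) repeats it: "The 6MWT at Baseline must be conducted prior to the first dose of oral treprostinil". The visit lists in Sections 7.2 and 7.3 add nothing about inhaled sessions, for the walk or for CPET.

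**After Baseline.** Section 3.3.1.2.2 says that later walks "should occur within 2-6 hours of the subject's last dose (i.e., most recent dose) of oral treprostinil". Sections 3.3.1.1 and 7.4.5 place the Week 24 CPET 2-6 hours after the morning oral dose. Section 1.2.3 supplies the pharmacology: "Maximum treprostinil concentrations occur between approximately 4 and 6 hours following administration of oral treprostinil in adults".

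**Who is affected.** Section 4.1, criterion 7, for Cohort 2: "The subject must have been receiving inhaled prostacyclin for at least 90 days", with a stable dose for the last 30 days. On stopping inhaled drug, Section 6.1.2 says: "The transition must be completed by Week 4, or the subject will be withdrawn from the study". Section 7.4.2 still lists inhaled dose adjustment among the Week 3 activities.

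**Analysis.** Under SAP Section 10.3, changes in distance are to be "summarized by cohort and compared within cohort using a Wilcoxon signed-rank test". SAP Section 10.2 uses a paired t-test for CPET changes, and Section 10.4 summarises Borg change. All p-values are labelled descriptive. Tyvaso and Ventavis dosing before each walk is listed. Dosing before CPET is listed and also summarised by cohort (Table 14.2.2.3).

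**The concern.** The Cohort 2 comparison is paired, with each child as his or her own control. It isolates the switch only if both measurements are taken at comparable points of the drug effect, or if the difference in timing is known. Here one side has a drug-timing rule and the other has none. A Baseline walk may come shortly after an inhaled session, long after one, or before the first session of the day.

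Protocol Section 1.4 expects clinical improvement from Baseline in this cohort, and no control arm would show a timing artefact. Other sources of variation are held fixed: oxygen flow and mode, the tester, and a practice walk where needed. For Cohort 1 pharmacokinetics, Section 3.3.3.1 even matches the Baseline start time to the expected Week 24 dosing time. The Borg score is taken with the walk and shares the gap.

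**Working it through.** The plan states no figure on this point and no power calculation, so there is nothing to reproduce. The check sets the timing rules side by side and then illustrates what an offset would do.

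**1. Timing rules for Cohort 2**

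| Assessment | Set time from inhaled session | Set time from oral dose |
|---|---|---|
| Baseline 6MWT and Borg | none | before the first dose |
| Week 3 6MWT and Borg | none, though inhaled drug may continue | 2-6 h |
| Week 6, 12, 24 6MWT and Borg | inhaled drug stopped | 2-6 h |
| Baseline CPET | none | before the first dose |
| Week 24 CPET | inhaled drug stopped | 2-6 h after the morning dose |

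The Week 3 visit is Day 22 ± 5, that is Days 17 to 27. All of these fall before Day 29, the Week 4 day in Table 3-1.

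**2. Why only Cohort 2.** Cohort 1 is on continuous infusion at Baseline and Cohort 3 is on no prostacyclin. Cohort 2 takes its drug in separate sessions, recorded as sessions per day (SAP Section 9.4.4).

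**3. How wide the oral window is.** Intervals are about 6-8 h (TID) or 4-6 h (QID) in Protocol Section 6.1.
- TID: 4 of 8 h = 50%, to 4 of 6 h = 67%.
- QID: 2 of 4 h = 50% (hours 2 to 4), to 4 of 6 h = 67%.

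The window contains the adult peak range of 4-6 h, but also hours 2 to 4. It is not a peak-only window.

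**4. Direction and size of an offset.** Assume no true difference between treatments at matching points of their dosing cycles. Let *d* be the walk difference between peak and trough, *f* the share of Baseline walks at peak (the rest at trough), and *u* the level of later walks as a fraction of *d* above trough, between 0 and 1. Then

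bias in mean change = (*u* − *f*) × *d*

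- *d* = 20 m, *f* = 0.5, *u* = 0: (0 − 0.5) × 20 = −10 m, which hides benefit.
- *d* = 20 m, *f* = 0.5, *u* = 1: (1 − 0.5) × 20 = +10 m, which mimics benefit.
- *d* = 10 to 30 m: the extremes run from −*d* to +*d*, so ±10 m to ±30 m.

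The documents give none of *d*, *f* or *u*; 10-30 m is an assumed range. For scale, Protocol Section 1.2.4 reports 11 m and 10 m in the two adult studies on background therapy.

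**5. Effect on the descriptive p-value.** Two-sided Wilcoxon signed-rank test, normal changes, no true effect, a uniform timing shift, 3,000 simulated trials per setting. n = 10 and 15 come from Protocol Section 10.2. The SD of change is assumed at 60 and 40 m; where two values are shown, they are for 60 and 40 m, lower value first.

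| Shift | P(p<0.05), n = 10 | P(p<0.05), n = 15 |
|---|---|---|
| 0 m | 4.0-4.7% | 4.7% |
| 10 m | 7.4-9.5% | 8.9-14.1% |
| 20 m | 15.8-29.0% | 21.9-40.6% |
| 30 m | 26.6-54.6% | 42.5-74.6% |

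At 0 m the spread is simulation noise rather than an effect of SD. A negative shift gives the same rates, because the test is two-sided.

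**The case against.** A reader might infer that Baseline sits near trough and follow-up near peak, so the design manufactures improvement. The documents do not support that. They leave Baseline timing open rather than placing it at trough, and a Baseline soon after a session could hide benefit instead. Follow-up is not confined to the peak either: the window covers half to two thirds of a dosing interval, the tablet is extended release, the 4-6 h figure is from adults, and the rule says should rather than must.

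Other objections have weight. The documents give no onset, duration or peak-to-trough walk difference for inhaled prostacyclin, so any size is assumed. The +23 m adult effect is a poor yardstick, because those patients were on no PAH therapy. The endpoints are secondary, the p-values descriptive, and no decision hangs on p<0.05. Even with perfect timing, an open-label study without controls could not attribute a walk change to the drug. Some of the information needed is already listed or tabulated.

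Finally, a fixed interval after inhalation would not match 2-6 h after an oral tablet, and one interval may not suit both Tyvaso and Ventavis.

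All this limits the strength of the point without removing it. The timing gap is in the text, and no planned analysis uses time since inhalation. The LOCF analysis deals with missing walks, not timing. SAP Section 12 names the date and time of the last inhaled dose for the pharmacokinetic listing. The walk listing in Section 10.3 refers only to dosing information, so later repair is not assured.

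**Conclusion.** The point holds as a limited one. In Cohort 2, change from Baseline in 6MWD, Borg score and CPET may combine assessment timing with the effect of the switch. The Week 3 walk carries a second unset interval when inhaled drug is still in use. The sign is unknown and the size cannot be derived from the documents. Under the assumed 10-30 m swing, an offset could equal or exceed the adult add-on effects, but that rests on the assumption and not on trial data.

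Nothing here touches the primary endpoint, which is transition by Week 4 and maintenance through Week 24. Cohorts 1 and 3 are not affected in this way. The change is a worthwhile, inexpensive improvement, not a condition for the study's main conclusion.

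**What to change.** **Protocol.** Set one assessment window, defined per inhaled product if needed, from the last inhaled session to the Cohort 2 Baseline 6MWT and CPET. Apply it to the Week 3 walk when inhaled therapy continues. Schedule the tests around existing sessions, with no change to inhaled dosing, and record the session time in the eCRF.

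**SAP.** For Cohort 2, tabulate time since the last inhaled session at each affected assessment. Repeat the 6MWD and CPET change summaries in subjects inside the window. State that the remaining timing differences between inhaled and oral assessments limit interpretation.

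The window makes Baseline timing consistent and visible; it does not make the two sides equivalent. If Cohort 2 Baseline visits are already done, the SAP part can still use whatever session times were recorded.

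**Cost.** Minor visit scheduling, one eCRF field, one table and one repeat summary. The subset summary will be imprecise: about 25 subjects are shared between Cohorts 1 and 2 (Protocol Section 3.5), with no fixed number for Cohort 2.

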3.3.1.2.2 Treatment Six-Minute Walk Tests

The 6MWTs will be conducted during each day of the inpatient hospital stay (Cohort 1 subjects only) and all subsequent study visits, and should occur within 2-6 hours of the subject's last dose (i.e., most recent dose) of oral treprostinil. Subjects receiving supplemental oxygen during the Baseline 6MWT must continue to receive the same flow rate and mode of oxygen therapy at all subsequent 6MWT assessments. The 6MWT should be performed at least two hours prior the CPET at Week 24/Premature Termination.

3.3.1.3 Borg Dyspnea

The Borg dyspnea score will be assessed prior to and following the completion of each 6MWT. The Borg dyspnea score is a 10-point scale rating the maximum level of dyspnea experienced during the 6MWT (Section 15.1). Scores range from 0 (for the best condition) to 10 (for the worst condition).

3.3.1.4 PAH Symptoms

PAH symptoms (fatigue, dyspnea, edema, dizziness, syncope, chest pain, orthopnea) will be assessed at the Baseline visit prior to the initiation of oral treprostinil dosing and at all subsequent visits, including each day of the inpatient hospital stay (Cohort 1 subjects only). Scores range from 0 (for the best condition) to 3 (for the worst condition).

3.3.1.5 Functional Classification

Subject clinical status will be assessed at Screening, Baseline, and all subsequent study visits. Functional classification will be recorded according to the Panama functional classifications for children with pulmonary hypertension and the WHO functional classification. Functional classification scales are provided in Section 15.2.

3.3.1.6 *N-terminal pro-BNP*

Plasma N-terminal pro-BNP concentration is a useful biomarker for PAH as it is associated with changes in right heart morphology and function [Fijalkowska, 2006]. NT pro-BNP
sample collection will occur at Baseline (or as part of the Screening visit assessment if the Screening and Baseline visits are combined) prior to starting oral treprostinil and repeated at Week 12 and Week 24/Premature Termination. Blood for NT-pro-BNP assessment must be drawn prior to conducting the 6MWT or CPET.

3.3.1.7 Pediatric Quality of Life Inventory (PedsQLTM)

Health-related quality of life will be assessed via the 23-item PedsQL questionnaire at Baseline (or as part of the Screening visit assessment if the Screening and Baseline visits are combined), Week 12, and Week 24/Premature Termination. The appropriate questionnaire must be administered based upon the subject's age group and in accordance with the questionnaire administration guidelines. The PedsQL must be completed as the first assessment (after informed consent is obtained) before the respondents complete any other health data forms, and before they see their physician/healthcare provider or have other assessments performed. An example of the PedsQL is provided in Section 15.3.

3.3.2 Safety

During this study, treatment emergent changes in physical findings, vital signs, clinical laboratory parameters, and the development of AEs will be the primary assessments of safety.

3.3.2.1 Medical History and Physical Examinations

A complete medical history, demographics, PAH history, and physical examination will be conducted at Screening. If any changes to the medical history occur between the Screening and Baseline visit, those should be recorded. Significant past or present illnesses, current prescription or nonprescription medications (including vitamins and herbal products), and history of medication allergies should be recorded. Any significant changes to the subject's medical condition, physical examination, and concomitant medications must be documented throughout the course of the study.

A complete physical examination will be conducted by a physician at Screening and at Week 24/Premature Termination. All treatment emergent clinically significant findings during the study will be reported as AEs.

TDE-PH-206

